## 7. Study Statistics

a. Primary outcome variables. The primary outcome variables are self-reported ratings of drug high and liking, changes in pupil diameter and blood pressure, pain threshold on 2 laboratory measures of pain, and analgesic efficacy in response to laboratory-induced pain. We expect that individuals with the minor allele of the A118G SNP and other

tagging SNPs across the OPRM1 gene will find hydromorphone more reinforcing (e.g., higher self-report ratings of high and drug-liking) and exhibit greater opioid-induced physiological changes (e.g., pupil diameter, blood pressure). Research also suggests the OPRM1 gene may also confer greater sensitivity to the negative effects of opioids, which may be observed as measuring greater ratings of nausea. We also hypothesize the minor allele and other tagging SNPs across the OPRM1 gene will produce higher pain threshold on 2 laboratory measures of pain, and lower analgesic efficacy in response to laboratory induced pain.

**b. Secondary outcome variables.** Decreases in cortisol levels as a function of the degree of pleasant effects of hydromorphone and painful stimuli, delay-discounting curves, and the effect of sex on all outcome measures. We hypothesize that individuals with the minor alleles will have greater decreases in cortisol levels as a function of the degree of pleasant effects of hydromorphone, lower cortisol in response to painful stimuli, and steeper discounting curves on a delay-discounting task. Finally, although we expect that the A118G will be associated with these effects, we hypothesize that several of the additional OPRM1 tagging SNPs will contribute to effect magnitude.

**c. Statistical plan including sample size justification and interim data analysis:** The aims of the proposed study will explore the impact of genetic variation across the OPRM1 gene on hydromorphone response. There are specific steps we describe below to assure that we interrogate all known functional variation across the OPRM1 gene, adequately cover all other variation using appropriately selected tagging SNPs, prevent spurious associations due to population stratification by accounting for local ancestry, and properly control the Type I error rate.

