**Association Model:** Our primary goal is to demonstrate the impact of SNP variation across OPRM1 on variability in response to hydromorphone across time and dose. Association analyses will be performed by modeling genotype at each SNP in a general linear model. In its simplest form this test, commonly termed the measured genotype analysis (137), models the influence of genotypic variation at a given locus on variation in the quantitative trait, essentially a one-way Analysis of Variance (ANOVA). This approach provides a distinct advantage in that it can easily be extended to a two-way ANOVA to model genotype effects across 3 different doses of drug. In addition, the flexibility of the GLM allows incorporation of ancestry covariates and environmental moderators or mediators. We will examine the impact of OPRM1 at each time-point in separate analyses and account for the multiple testing using LD-adjusted Bonferroni correction (see below).

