**Power and Correction for Multiple Testing:** Power (1-Type II error) and correction for multiple testing (control of Type I error) are important considerations in any genetic association study. Typically investigators attempt to control the Type I error rate of a given set of hypothesis tests by controlling the family wise error rate through manipulation of the alpha level of the test. This is not problematic when a handful of tests are performed at an alpha level (false positive level) of 5%, where the usual approach is the Bonferroni correction. We anticipate performing tests across multiple time-points and must adjust our target alpha level. Importantly, our 71 selected SNPs across the OPRM1 gene (see below) do not represent 71 independent tests due to correlation between SNPs. We will use an approach, termed SNPSpD (138) which uses spectral decomposition to estimate the number of independent tests across the region. Using available HapMap data, we estimate 44 independent tests across the region. We calculate power for the GLM approach modeling the effect of genotype on phenotype. If we assume a constant effect size difference between genotype groups (at each dose other than placebo), at an alpha level conservatively adjusted for 50 tests to .001, using the entire completer sample (N= 100) or the sex subsamples (N=50), we have >80% power for modest effect sizes of ~.45 and .67 respectively. In our calculations, effect size (Cohen's d) is the mean difference between genotype groups in standard deviation units. Importantly, this effect size is well within the range seen by other studies examining drug response difference in OPRM1 (e.g., Ray et al., 2004: effect size = 1.2).

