**Analysis of pain testing sessions:** We hypothesize that OPRM1 SNP variants will exhibit greater pressure pain thresholds, greater CPM efficiency, lower hydromorphone-related analgesia, and lower cortisol stress response than participants with the major allele, and that results will be positively correlated with response to self-report and physiologically-mediated hydromorphone drug effects collected during days 3-5. Pressure pain threshold will be estimated by averaging the results of the 2 administrations to radiobrachialis and quadriceps muscle groups. We will generate a CPM index for each participant [(mean pressure pain threshold during cold pressor)/(mean pressure pain threshold prior to cold pressor)] x 100 (90). These values will provide a quantitative measure of percent change in the test stimulus (i.e., pressure point threshold). Mixed effects regression models with a random intercept will be used to compare dependent variables (pressure pain threshold, DNIC threshold, DNIC index) as a function of within-subject drug effects (placebo vs. hydromorphone), and between-subject effects of OPRM1 SNP analysis will be conducted as specified in Aim 1. Gender, age, and race have been associated with response to pain and the CPM test (146-148). Gender will be evaluated using independent subgroup analyses and age and race will be included as covariates. Finally, subscale scores of self-report measures of pain and coping strategies will be compared between the two genotype groups using independent samples t-tests, and drug identification data will be compared using a chi-square for each drug condition. We expect that both experimental manipulations will induce pain in the minor and major allele groups, and that participants with the minor allele will demonstrate lower sensitivity to pain (e.g., greater pressure pain magnitudes), lower NRS ratings of pain, lower cortisol response to painful stimuli, and lower analgesic relief from hydromorphone compared to the major allele participants.

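### Section 7b predicts that tagging SNPs add to the A118G effect, but section 7c tests each SNP only in its own model, so a SNP that is merely correlated with A118G can be read as an added contributor

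*Combined protocol and SAP*

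**What the plan says.** Section 7b (Secondary outcome variables) closes by expecting an A118G association and adding that "we hypothesize that several of the additional OPRM1 tagging SNPs will contribute to effect magnitude". Set against an expected A118G effect, this most naturally means a contribution over and above A118G, although the section does not say so outright.

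Section 7c (Association Model) gives the method: "Association analyses will be performed by modeling genotype at each SNP in a general linear model". In its simplest form the test "models the influence of genotypic variation at a given locus on variation in the quantitative trait", and it is extended to model genotype across doses. Of further terms it says that "the flexibility of the GLM allows incorporation of ancestry covariates and environmental moderators or mediators"; a second SNP is not among them. The pain analyses follow the same route: "between-subject effects of OPRM1 SNP analysis will be conducted as specified in Aim 1", with age and race as covariates and gender handled by subgroup.

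On correlation between SNPs, section 7c (Power and Correction for Multiple Testing) states that "our 71 selected SNPs across the OPRM1 gene (see below) do not represent 71 independent tests due to correlation between SNPs" and continues: "Using available HapMap data, we estimate 44 independent tests across the region". Alpha is then set at .001, allowing for 50 tests. Under SNP selection, tags were chosen at an r2 of 0.8, with predicted functional variants above a frequency of .03 forced in. Local ancestry is re-estimated for each association without the tested SNP.

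Nowhere does the plan give a conditional, joint or haplotype test, or a rule for deciding that a tag adds to A118G.

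**The concern.** A single-SNP model asks whether a SNP is associated with response. It cannot say whether that SNP matters once A118G is known. When two SNPs are correlated and one has an effect, the other shows a diluted copy of it. The plan acknowledges that its SNPs are correlated, and its selection threshold allows a retained tag to share substantial r2 with A118G.

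The two places where the plan deals with correlation do not fill this gap. The spectral decomposition method counts effective tests, which controls false positives when nothing is associated. The local ancestry adjustment deals with population stratification. Neither separates a tag's own effect from its correlation with A118G.

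The gap opens in the case the investigators expect, a real A118G effect. The stake is then a statement about which OPRM1 variants matter: tags could be credited with adding to the effect when they only mark A118G.

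**Working it through.** **The plan's own figures.** Alpha: 0.05/50 = .001, which reproduces. Power: the plan states more than 80% at d of about .45 with N=100. With one value per person, equal genotype groups and a two-sided test I get 14.9%. Counting three active doses per person as independent observations gives 72.8%. The plan does not state the within-person correlation or the sidedness of the test. That mismatch is a separate matter and does not decide this point.

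**Inputs.**
- From section 7c: N=100; alpha .001; d=.45 (planning effect); d=1.2 (effect cited from an earlier OPRM1 study).
- Assumed, not in the documents: carrier share q=.30; d=.8 as a middle value; one value per person; two-sided tests; r2 between tag and A118G of .2, .5 and .8; a tag with the same carrier share and no effect of its own; no ancestry covariate.

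**Formula, tag tested alone.**
1. Share of variance explained by A118G: R2 = q(1−q)d² / (1 + q(1−q)d²).
2. Share picked up by the tag: r2 × R2.
3. Noncentrality: λ = N·r2·R2 / (1 − r2·R2).
4. Rate = probability that a noncentral F with 1 and 98 df exceeds 11.51, the .001 critical value.

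Worked case, d=.8 and r2=.5: q(1−q)d² = .21 × .64 = .1344; R2 = .1344/1.1344 = .1185; tag share = .0592; λ = 100 × .0592/.9408 = 6.30; rate = 19.8%.

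| A118G effect | R2 | A118G itself significant | Tag, r2=.2 | Tag, r2=.5 | Tag, r2=.8 |
|---|---|---|---|---|---|
| d=.45 | .041 | 10% | 0.8% | 3.0% | 6.6% |
| d=.8 | .118 | 61% | 3.8% | 19.8% | 44.3% |
| d=1.2 | .232 | 98% | 12.6% | 59.2% | 91.2% |

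A simulation with 20,000 trials per cell and correlated binary carriers agrees within about 1.5 percentage points in every cell.

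**Sensitivity to carrier share.** At r2=.5, moving q from .20 to .50 moves the rate from 2% to 4% (d=.45), 13% to 26% (d=.8) and 43% to 69% (d=1.2).

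**Sensitivity to the power for A118G.** Averaging over repeated doses would raise power for A118G, and the tag rates with it. With A118G sized for 80% power (normal approximation), simulation at carrier shares of 20% to 50% puts the tag rates at about 5–6%, 28–30% and 57–59% for r2 of .2, .5 and .8.

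**With A118G in the model.** The same tag is significant in about 0.1% of simulated trials in every setting, which is the nominal alpha.

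**Price of conditioning.** For a tag with a genuine effect of its own of d=.8 and q=.30, λ = N·q(1−q)d²(1−r2) with 1 and 97 df. At r2=.5, λ = 100 × .21 × .64 × .5 = 6.72 and power is 22%. At r2=.8, λ = 2.69 and power is 4.5%.

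**The case against.** The strongest reply is that the main hypotheses are marginal. Sections 2 and 7a say that the A118G minor allele and the tags will predict response, and section 7c states its goal as the impact of variation across the gene. Single-SNP models answer that. The contribution statement is one sentence under secondary outcomes, and no primary test or sample size depends on it. This stands, and it limits the weight of the point.

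A reader might infer that correlated tags will be reported as added contributors. The documents do not support that. They never say that a single-SNP hit counts as an added contribution; they leave the question without a rule. The supportable statement is that such a tag can be significant and can be read that way.

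A reader might also infer a high error rate from the 0.8 tagging threshold. That threshold permits high r2 but does not show that it occurs, and the plan gives no tag's r2 with A118G. Most selected tags should lie below 0.8 with A118G; forced-in functional variants, and differences between the reference panel and the study sample, could be exceptions. Rates at an alpha of .05 would be much larger, but .05 is not the plan's threshold. Nor can the chance that at least one of the 70 other SNPs is a false contributor be fixed: 44 effective tests among 71 SNPs describes correlation across the whole region, not with A118G.

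The ancestry estimate for a tag may draw on A118G, since only the tested SNP is dropped. My calculation omits that covariate. Including A118G in an ancestry estimate is still not the same as conditioning on it.

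Finally, conditioning on A118G presumes nothing about causality only if it is reported with care: a tag that survives may mark another variant, and one that fails may simply be inseparable from A118G. Joint or haplotype models would also be acceptable.

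**Conclusion.** The point holds in a limited form. The plan states a hypothesis of added contribution and gives only an analysis that cannot distinguish it from correlation with A118G. At the plan's N and alpha, the chance that a tag with no effect of its own is significant runs from about 1% (d=.45, r2=.2) to about 91% (d=1.2, r2=.8), against about 0.1% with A118G in the model. Only N, alpha and the d values of .45 and 1.2 come from the documents. Carrier share, r2, d=.8, one value per person and two-sided testing are assumptions, so the range should not be read as a forecast for any particular tag.

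The tests of whether A118G and each tag are associated with response stand as planned. This is an inexpensive improvement to a secondary hypothesis, not a change that the trial's main conclusions require.

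**What to change.** In section 7c:
- Keep the single-SNP scan and label it as the marginal result.
- For each tagging SNP, also fit the same GLM with A118G as a covariate, at the same LD-adjusted alpha.
- Base any claim that a tag contributes beyond A118G on the conditional term. A prespecified joint or haplotype model would serve the same purpose.
- State that tags in high LD with A118G may not be separable from it, so a non-significant conditional term does not show that A118G is the causal variant.
- Report each tag's r2 with A118G in the study sample beside both results.

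The cost is a few sentences and one extra model per tag and outcome, with no new data. The statistical price is low conditional power for tags in high LD (22% at r2=.5 and 4.5% at r2=.8 for a true d=.8, as worked above), which reflects how little the data can say about such tags. The text should be added before genotype results are analysed.

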#### 4. Study Procedures

- a. Study design, including the sequence and timing of study procedures (distinguish research procedures from those that are part of routine care).

**Study Overview:** This study will be a between-group (total completer N=100) evaluation of genotype and sex, and a within-subject evaluation of opioid dose-response. The study will be conducted over 5 days (4 nights) at the Behavioral Pharmacology Research Unit (BPRU) and a residential clinical research unit (CRU) (Figure 1). Day 1 will be an Admission day. Days 2-5 will consist of blinded study drug administration in the morning, 1 pain testing session, and self-report/physiological measures of drug effects for 6 hours post dosing. Participants will receive double-blind doses of oral hydromorphone (2mg, 4mg, 8mg) (99-102) or weight and color-matched placebo in a randomized, counter-balanced research design.

**Screening Visit:** Participants will complete a brief phone screen to determine initial eligibility and will be invited to complete an in-clinic screen. Participants will sign an informed consent form with a study staff member to begin the Screening visit. To reduce expectancy effects, the consent will inform participants the study drug may consist of one or more of numerous different drug classes (e.g., opioids, stimulants, over-the-counter medications), a common practice in laboratory based studies of drug effects (103, 104). Following consent, a staff member will administer a battery of measures to establish study eligibility (see Study Measures below). A urine sample will be collected and tested for evidence of illicit drugs and to establish medical eligibility. A blood sample of no more than 2 tablespoons will also be collected from eligible participants for medical and genotype analysis. Participants will also be asked to provide a second blood sample (2 additional tablespoons) that will be collected at either Screening or Admission and stored for future genetic analysis. This will be voluntary. Participants who meet eligibility criteria (including results of laboratory blood tests) will be scheduled for an Admission day.

**Study Day 1, Admission Visit:** Participants will complete a brief history and physical to determine final study eligibility and will be admitted to the CRU for 5 days (Admission day + 4 session days). During the Admission day, participants will be familiarized with the pain testing procedures and the measures used during session days 2-5.

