We have chosen to deliver doses lower than those administered by that study so we may evaluate whether there are individual differences in the ability to detect the low dose of hydromorphone. Participants in our study will receive three active hydromorphone doses. The first dose participants will receive is the mid-level dose, which will be administered on study Day 2. Any participant who has a negative reaction to this dose will be discharged from the study. The participants will receive placebo, low, and high doses on Days 3-5 of the study; the order of doses will be randomized and counter-balanced. These doses were deemed safe in the same participant population in the Walsh study, they produced a documented detectable range of subjective effects, and they represent suprathreshold doses consistent with those abused recreationally. Ultimately, we feel confident these dose values do not impose any unique risk above and beyond that presented by the administration of hydromorphone.

Generic powdered hydromorphone will be encapsulated using size 0, opaque, hard gelatin capsules; placebo will be size and weight matched and will contain microcrystalline cellulose filler. A pharmacy member with no participant interaction will conduct the dose randomization. All medication administration will be supervised and a medical staff member will be available to address any adverse events or to break the medication blind.

- b. Justification and safety information if FDA approved drugs will be administered for non-FDA approved indications or if doses or routes of administration or participant populations are changed.

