**SNP selection (for association testing and control of Local Ancestry):** SNPs will be genotyped across the OPRM1 region to allow us to test associations across the gene and account for genetic ancestry (ethnicity). Typing all available SNP markers across the candidate gene set is inefficient and not necessary since many will provide redundant information due to linkage disequilibrium (LD). A more cost-effective strategy is to select a subset of representative SNPs (tagSNPs) that are in strong LD (measured through pairwise  $r^2$ ) with other SNPs that are therefore not required for genotyping in order to capture the haplotypic diversity across the gene. We followed this approach across OPRM1 with the Tagger algorithm at an  $r^2$  value of 0.8 and a minor allele threshold of 0.05 (139). We force included all predicted functional variation with allele frequency > .03 to allow for secondary hypothesis testing across OPRM1 functional SNPs. We used the latest Data release 21 (CEU Sample) of HapMap (<http://www.hapmap.org>) in conjunction with the NCBI build 35/hg17 of gene and EST data at UCSC Genome Browser (<http://genome.ucsc.edu/cgi-bin/hgGateway>). Using this approach, we selected 71 SNPs across the OPRM1 region for association testing and control of local ancestry. In our approach, we will re-estimate local ancestry for

each SNP association, dropping the tested SNP from ancestry estimation. Our approach to accounting for population stratification is detailed below.

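### The stated >80% power at Cohen's d of .45 (N=100) and .67 (N=50) cannot be reproduced from the stated inputs and is not delivered by the genotype model described, whose contrast and participant error term are not named

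*Combined protocol and SAP*

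**What the plan says.** Section 4a (Study Overview) makes genotype a between-person factor and describes "a within-subject evaluation of opioid dose-response", so every completer contributes a value at each dose.

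Section 7c (Association Model) tests each SNP in a general linear model, in its simplest form a one-way ANOVA. Its only statement on combining doses is that "it can easily be extended to a two-way ANOVA to model genotype effects across 3 different doses of drug". No participant effect or repeated-measures error is named there. Time-points are analysed separately, so nothing is averaged over time.

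Section 7c (Power and Correction for Multiple Testing) adjusts alpha to .001 for 50 tests. It sets out the effect pattern with "If we assume a constant effect size difference between genotype groups (at each dose other than placebo", defines the metric by "effect size (Cohen's d) is the mean difference between genotype groups in standard deviation units", and concludes that "we have >80% power for modest effect sizes of ~.45 and .67 respectively", the two values being for 100 completers and for 50 of one sex. It gives no within-person correlation, tested contrast, genotype split or sidedness.

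Section 7c (Analysis of pain testing sessions) does name a random-intercept mixed model for the pain measures, but sends their SNP test back to the method of Aim 1.

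**The concern.** The power paragraph supplies almost enough to check it, and the obvious check falls far short of 80%. If the statement is wrong as written, a null result could be read as ruling out a difference of .45 SD that the study had little chance of detecting.

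The unnamed error term bears on the same test. Section 7c makes response over time and dose its main goal and promises control of false positives. With repeated values per person, that control depends on judging genotype against between-person variation. The text does not say that this will be done for the drug-effect outcomes.

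**Working it through.** **Inputs from Section 7c:** alpha = .05/50 = .001; N = 100 and 50; d = .45 and .67; the same d at every active dose. Because d is in SD units, the single-dose SD is 1.

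**Assumed, because not stated:** a two-sided test; equal genotype groups (the most favourable split); equal variance at each dose; a common correlation ρ between a person's doses, shown at .3, .5 and .7.

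**Formula:** power is the chance that a noncentral F with 1 and N−2 df exceeds its .001 critical value (11.51 at N=100, 12.29 at N=50). The noncentrality is λ = d² / [v(1/n₁ + 1/n₂)], where v is the variance of the per-person quantity tested.

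**1. The plan's own figure, one value per person (v = 1).**
- N=100: λ = .2025/.04 = 5.06, power 13.5%.
- N=50: λ = .4489/.08 = 5.61, power 14.6%.

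The stated >80% does not reproduce. Even at alpha .05 the results are 61% and 64%.

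**2. Mean of three active doses, v = (1+2ρ)/3.**

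| ρ | v | λ, N=100 | power | λ, N=50 | power |
|---|---|---|---|---|---|
| 0 | .333 | 15.19 | 69% | 16.83 | 72% |
| .3 | .533 | 9.49 | 38% | 10.52 | 41% |
| .5 | .667 | 7.59 | 27% | 8.42 | 29% |
| .7 | .800 | 6.33 | 20% | 7.01 | 21% |

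Power falls as ρ rises, so the first row is the ceiling for non-negative correlation. A one-sided test raises that ceiling only to 76% and 79%.

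**3. Other readings that might have produced >80%.**

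| Reading | N=100 | N=50 |
|---|---|---|
| Three doses counted as independent people (v = 1/3, 3N−6 df) | 72% | 77% |
| .45/.67 taken as Cohen's f, two groups (λ = f²N = 20.25; 22.45) | 86% | 88% |
| The same, three genotype groups | 77% | 79% |
| Active mean minus placebo, v = (1+2ρ)/3 + 1 − 2ρ, at ρ .3/.5/.7 | 15/27/57% | 16/29/60% |
| Active mean with placebo as covariate, v = (1+2ρ)/3 − ρ², N−3 df, at ρ .3/.5/.7 | 50/54/74% | 53/57/76% |

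Both placebo-adjusted rows assume no genotype difference at placebo. The change score reaches 80% at ρ of about .79 (N=100) and .78 (N=50). The covariate form reaches it at about .74 and .72. With three groups, 80% power needs f = .46 and .68, close to the printed values, but the text says d.

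**4. Detectable d at 80% power, equal groups.**
- One value per person: .85 (N=100) and 1.24 (N=50).
- Three-dose mean at ρ .3/.5/.7: .621/.694/.760 and .905/1.012/1.108.

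**5. Unequal groups.** With an assumed 20/80 split, one value per person gives 6% and 7%. The three-dose mean gives 19/13/9% and 20/14/10%. SNP selection used an r² "value of 0.8 and a minor allele threshold of 0.05". At that floor, carriers number 1 − .95² = 9.75% (assuming Hardy-Weinberg and carrier coding). Power is then 2% to 3% with one value and 3% to 7% with the mean. That is the edge case, not the typical SNP.

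**6. Error term, only if doses were stacked as separate rows.** The variance of the genotype difference is understated by a factor of 1+2ρ. True size at nominal .001 is then about 2[1 − Φ(3.29/√(1+2ρ))]:
- ρ = .3: 3.29/1.265 = 2.60, size .009.
- ρ = .5: 3.29/1.414 = 2.33, size .020.
- ρ = .7: 3.29/1.549 = 2.12, size .034.

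Simulation of 20,000 null trials at N=100 gave .010, .019 and .033.

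**7. Doses and days.** Section 6a says "The first dose participants will receive is the mid-level dose, which will be administered on study Day 2" and "The participants will receive placebo, low, and high doses on Days 3-5 of the study". The Association Model refers to three doses without naming them, while the pain analysis refers to drug effects from days 3 to 5. Three active doses would include Day 2; days 3 to 5 would leave placebo, low and high. If only low and high entered the mean, v = (1+ρ)/2 and power would be 28/22/18% and 30/24/19%.

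**The case against.** The strongest reply is that power depends on how the doses are modelled, and that a placebo-referenced test is natural here. The effect is assumed only at active doses, placebo is included as the comparison, and Section 7c says the linear model can take covariates. Over the same correlation range, the covariate analysis gives up to 74% and 76%. That stands as a limit: the shortfall has no single size, and a reader might wrongly infer a several-fold overstatement under every valid model. It does not rescue the text, because Section 7c states neither the contrast nor the high correlation needed.

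A second reply is that saying a model can be extended to a two-way ANOVA describes flexibility and does not commit to stacking rows. This also stands. Section 4a calls dose within-subject, and the pain analysis uses a random intercept, so the authors recognise repeated data. A reader might infer that the trial plans an invalid test with inflated false positives; the documents do not show that. Tests at a single dose or on a per-person summary are unaffected.

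Third, everyone takes the mid dose on Day 2, so a reader who infers that genotype comparisons at that dose are confounded with day would be wrong. Only contrasts between the mid dose and other doses are.

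Finally, most detectable effects in step 4 are below the 1.2 that the plan cites from an earlier study. The exception is 1.24, for one value per person at N=50.

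**Conclusion.** The power statement is wrong as written for the model described. At the stated d, alpha and N, power is 14% and 15% with one value per person. For the three-dose mean it is 20% to 38% (N=100) and 21% to 41% (N=50), with a ceiling of 69% and 72%. These figures rest on equal genotype groups and a two-sided test; the ranges also rest on correlations of .3 to .7, but the ceiling needs only a non-negative correlation. Unequal groups lower them all.

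The documents do not settle how >80% arose. A mislabelled Cohen's f, dose rows treated as independent, or an unstated placebo-adjusted contrast with a high correlation are all possible. Confidence is high that the figure cannot be reproduced. The error-term point is a risk to close and the dose-and-day point a matter of clarification; neither is a demonstrated error of analysis.

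**What to change.** In Section 7c:

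- Name the contrast tested for genotype across doses, and a participant-level error term: the random intercept already named for pain, a repeated-measures ANOVA, or a per-person summary. Say that this also applies to the SNP tests on pain outcomes that are referred back to Aim 1.
- Confirm whether .45 and .67 are d or f. Restate the power, or the detectable d, for the named model with its assumed correlation and genotype split. If a placebo-adjusted analysis was meant, state it and justify the correlation it needs.
- State which doses and days enter the model, reconciling Sections 6a and 7c. Note that between-dose contrasts involving the mid dose are confounded with Day 2.

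The cost is wording and a recalculation in standard software, with no new data. The drawback is a less favourable stated effect: for the three-dose mean with equal groups, detectable d rises from .45 to about .62 to .76 at N=100, and from .67 to about .905 to 1.108 at N=50. Wording cannot remove the Day 2 confounding. No change to dosing or sample size is proposed.

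### The plan says alpha must be adjusted for separate time-point tests, but its only adjusted alpha (.001 for 50 tests), at which power is stated, covers a single 44-test SNP scan

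*Combined protocol and SAP*

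**What the plan says.** All of this is in section 7, Study Statistics, unless another section is named.

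- The introduction to the statistical plan undertakes to "properly control the Type I error rate".
- Association Model fits each SNP in a general linear model and notes that "it can easily be extended to a two-way ANOVA to model genotype effects across 3 different doses of drug". It then says: "We will examine the impact of OPRM1 at each time-point in separate analyses and account for the multiple testing using LD-adjusted Bonferroni correction".
- Power and Correction for Multiple Testing gives the reason: "We anticipate performing tests across multiple time-points and must adjust our target alpha level". It continues that "our 71 selected SNPs across the OPRM1 gene (see below) do not represent 71 independent tests due to correlation between SNPs", names SNPSpD as the method for counting effective tests and reports that "we estimate 44 independent tests across the region".
- The power sentence in that paragraph works "at an alpha level conservatively adjusted for 50 tests to .001". It claims more than 80% power for effect sizes of about .45 in all 100 completers and .67 in each sex subsample of 50.
- Section 4, Acute Effects of Hydromorphone, collects the acute measures before dosing and at no more than 15 times over the following 6 hours. How many of these enter the tests is not stated.

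No divisor for time-points appears anywhere, and no alpha is named as the threshold for declaring a result.

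**The concern.** The plan names a source of multiplicity, says alpha has to reflect it, and then supplies a count that does not contain it. SNPSpD works on the correlation between SNPs and has no time dimension, so 44 is the size of one scan of the gene at one time-point.

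Two things are at stake.

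1. The stated power belongs to a threshold looser than the plan's own reasoning requires, for any number of time-points above one.
2. An analyst cannot tell which threshold applies. With .001, .05/44 and .05/660 all arguable, the same SNP result could be called significant or not, and the choice could be made after the data are seen. A chance result for one SNP at one hour could then be reported as a corrected OPRM1 effect.

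**Working it through.** **Inputs from section 7:** base alpha .05; 44 effective SNP tests; .001 for 50 tests; N = 100. **From section 4:** at most 15 post-dose times. **Assumed, because the documents do not give them:** number of time-points analysed, T = 2, 6 or 15; correlation between time-points; two-sided tests; a 50 v 50 genotype split for detectable effects.

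**1. The plan's own figure.** .05/50 = .001, an exact match. One scan alone would give .05/44 = .00114.

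**2. Room in the allowance.** 50 − 44 = 6, and 50/44 = 1.14 scans. A second time-point makes 2 × 44 = 88 tests, for which Bonferroni gives .05/88 = .00057.

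**3. Divisor with time-points included,** .05/(44 × T):
- T = 6: .05/264 = .00019
- T = 15: .05/660 = .000076

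**4. Family-wise error for one outcome if .001 were the testing threshold.** For one SNP, let p(T) be the chance that at least one of T null tests passes .001. With T equally correlated normal statistics (correlation ρ) and c = 3.29,

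p(T) = 1 − ∫ φ(u) [Φ((c − √ρ u)/√(1 − ρ)) − Φ((−c − √ρ u)/√(1 − ρ))]^T du.

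Under independence p(T) = 1 − .999^T. The error over 44 effective SNP tests is 1 − (1 − p(T))^44. For example, T = 2 and ρ = .95 give p = .00143 and 1 − (1 − .00143)^44 = .061.

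| Time-points | ρ = .95 | ρ = .9 | ρ = .8 | independent |
|---|---|---|---|---|
| 1 | .043 | .043 | .043 | .043 |
| 2 | .061 | .067 | .075 | .084 |
| 6 | .096 | .122 | .158 | .232 |
| 15 | .129 | .181 | .263 | .483 |

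At ρ = .99 the values for 2, 6 and 15 time-points are .051, .064 and .075.

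**5. Detectable effect at 80% power.** Two-sided t-test, 50 v 50, 98 degrees of freedom, noncentrality d × √(50/2) = 5d:

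| Per-test alpha | Route | d |
|---|---|---|
| .00114 | one summary per outcome | .84 |
| .001 | as in the power sentence | .85 |
| .00019 | T = 6 | .95 |
| .000076 | T = 15 | 1.00 |

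This simple model does not reproduce the plan's figure of about .45. The d values compare the routes with one another and are not shifts from .45.

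**The case against.** The strongest defence is that the plan already promises the right correction. It names Bonferroni, ties it to the separate time-point analyses and brings in SNPSpD only to count correlated SNPs. A fair reading is Bonferroni over time-points combined with SNPSpD over SNPs, with T simply not filled in. That reading is open, and it means the plan cannot be said to ignore time-points. It does not remove the problem, because on that reading the .001 and the power attached to it are wrong for any T above 1.

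Four further points limit what can be claimed.

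- **A reader might infer that results will be declared at .001, with error of up to 48%.** The documents do not say so. The figure appears only in the power sentence, so every error rate in step 4 is conditional.
- **A reader might infer that the plan breaks a promise to control error across its primary outcomes.** Section 7a lists several: "The primary outcome variables are self-reported ratings of drug high and liking, changes in pupil diameter and blood pressure", followed by pain measures. The promised adjustment concerns SNPs and time-points, not phenotypes. Control within each phenotype is defensible, so the missing statement about outcomes is an omission of lesser weight.
- **Fifteen is a ceiling on collection, not an analysis schedule.** The pain measures come from one session a day, so multiplicity over post-dose times does not arise for them.
- **Time-points will be correlated.** This shrinks the error but does not remove it: at a correlation of .99, two time-points still give 5.1%.

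**Conclusion.** The point holds for time-points. The plan requires an alpha adjusted for multiple time-points, and the only adjusted alpha it gives has no room for a second one (88 tests against 50). The power is therefore stated at an alpha that lacks the required adjustment. This rests on the plan's own figures and needs no assumption about correlation.

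The consequence for false positives is conditional on .001 being the testing threshold: for one outcome, about 6-8% at 2 time-points, 10-23% at 6 and 13-48% at 15. It also rests on 44 effective SNP tests, equal correlation between time-points and a range from .95 to independence. The documents give neither the correlations nor T.

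The documents do not support a claim that error is uncontrolled, or that outcomes carry the same weight as time-points. Because this is the analysis the plan calls its primary goal, the threshold should be settled before any genotype test is run.

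**What to change.** Choose one route and write it into section 7.

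**(a) One summary per outcome and session.** Pre-state it, for example peak or area under the curve over 6 hours. Keep dose in the genotype model as Association Model intends, and name the single genotype test per SNP that counts. Show time courses descriptively. Test at .05/Meff within each phenotype, which is .0011 at Meff = 44. *Cost:* no formal test by time-point, so part of the goal of describing response over time is given up.

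**(b) Keep the time-point tests.** State T and use .05/(Meff × T), for example .00019 for T = 6 or .000076 for T = 15. Alternatively, use a max-statistic resampling method that keeps the local-ancestry covariates described under Population Stratification. *Cost:* with Bonferroni, and under the assumed 50 v 50 comparison, detectable d rises from .85 at .001 to .95 for T = 6 or 1.00 for T = 15. Resampling should cost less because it uses the correlation.

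**With either route,** restate alpha and power in Power and Correction for Multiple Testing, and say whether the sex-subsample tests, now powered at the same .001, fall inside the family.

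**Secondary note on outcomes.** Either state that control is within each phenotype and limit the Type I error claim to that, or add the number of primary outcomes to the divisor. The second option first needs an agreed list, since section 2 treats pain as the secondary aim while section 7a lists pain measures as primary.

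The work is a change of wording and a new power calculation.
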